We hypothesize this rehabilitation strategy will also be successful in human subjects. The proposed project aims to translate animal hemianopia research to a noninvasive rehabilitation system for use by human visual hemianopia patients. The specific objectives of the program can be enumerated as follows:

Specific Aim 1: Determine the efficacy of an intervention using cross-modal stimulation training to restore visual function in homonymous hemianopia patients.

Specific Aim 2: Assess the long-term effects of rehabilitation through follow-up visits after the completion of rehabilitation.

Methods and Measures

Design

This study will test a rehabilitation technique for treating visual hemianopia and compare results against measures from patients pre-intervention. We will recruit all interested patients with visual hemianopia and will assess visual field, visual capabilities, quality of life, and brain images as part of our research measures.

Setting

Rehabilitation training sessions and progress tests will be performed on the Wake Forest Baptist Medical Center Campus and in subjects' homes. Since administering the Humphrey visual field test requires specific equipment, subjects will visit an optometrist's office for these tests. Subjects will perform the remaining visual tests on the Wake Forest Baptist Medical Center Campus.

Subjects selection criteria

- **Inclusion Criteria**
 - Adult volunteers diagnosed with homonymous visual hemianopia / hemianopsia (ages 18-99)
 - MRI or CT scan demonstrating lesion in the occipital lobe of the brain and/or affecting white matter tracts that provide visual input to the occipital lobe of the brain
 - Brain injury due to ischemic or hemorrhagic causes that occurs after age 18 and at least 6 months prior to screening visit
 - Demonstration of good fixation on visual training task
- **Exclusion Criteria**
 - Volunteers who are unable to complete the study tasks or understand instructions
 - Subjects that are not able to provide written consent or verbal assent
 - Subjects who are not available to complete all rehabilitation sessions
 - Physical, neurological or mental disability that would interfere with study intervention
 - Concurrent participation in "vision therapy" other than standard occupational or physical therapy

- **Sample Size**

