The virtual reality headset and headphones will provide visual and auditory stimulation used in the rehabilitation training. Each rehabilitation session will consist of 200 trials. At the end of each rehabilitation session, subjects will perform a brief 2-minute VR visual field progress test with the VR system to track rehabilitation progress. The rehabilitation will be considered complete once patients can reliably detect stimuli 45° in the hemianopic field.

If patients cannot detect stimuli at 15° by the end of 30 days of rehabilitation, they will repeat the rehabilitation for one more month, in order to determine if the slow progress or lack of progress is caused by simply not spending enough time performing rehabilitation.

Study Session 63: Post Rehabilitation Tests - Subject visual field did not increase (1 hour)

If no visual field improvement (measured by virtual reality visual field progress tests) has occurred at the end of the 2nd round of rehabilitation, subjects will complete one last visit, where they will be given the

NEI VFQ-25 and VA LV VFQ-48 questionnaires to complete. This visit will occur on the Wake Forest Baptist Medical Center campus.

Study Session 33: Post Rehabilitation Tests - Subject visual field increase (1.5 hours)

If a subject shows visual field expansion in the virtual reality visual field progress test, subjects will be given a **Peripheral Visual Field Test, NEI VFQ-25 and VA LV VFQ-48 Questionnaires** in order to measure visual field expansion and improvements in quality of life.

In previous animal studies, rehabilitated hemianopic animals could only detect spatial frequencies of 2 cycles/degree compared to over 5 cycles/degree in the (normal) intact animals. We hypothesize the subcortical visual pathway mediating the restored visual functions may not have the same capabilities as the visual cortex it is replacing. Therefore, recovered vision may have lower visual acuity. The different pathways involved in cross-modal rehabilitation may also affect abilities for shape recognition in the newly recovered visual field. We will explore whether this is the case with a simple **shape recognition test, visual acuity test, and color vision test** during this visit. Subjects will complete this visit on the Wake Forest Baptist Medical Center campus.

Study Session 34: Humphrey Visual Field Post-Intervention Test (1 hour)

Subjects will report to an optometrist for a **Humphrey Visual Field** perimetry test.

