Study Session 35: 3 Month Post-Intervention Follow-up Tests (1 hour)

Subjects will complete a follow-up visit 3 months after the end of rehabilitation on the Wake Forest Baptist Medical Center campus. The follow-up visit will consist of a peripheral visual field test, and NEI VFQ-25 and VA LV VFQ-48 questionnaires.

Study Session 36: 6 Month Post-Intervention Follow-up Tests (1 hour)

Subjects will complete a final follow-up visit 6 months after the end of rehabilitation on the Wake Forest Baptist Medical Center campus. The follow-up visit will consist of a peripheral visual field test, and NEI VFQ-25 and VA LV VFQ-48 questionnaires.

Outcome Measure(s)

The primary outcomes for all participants will be the visual field measurements from Humphrey Visual Field and peripheral frame test, with comparisons made before (visits 1 and 2) and after treatment (visits 34 and 35 or visits 63 and 64).

Secondary outcome measures will include differences in quality of life questionnaire results from before (visit 1) and after treatment (visit 33 or 63) and changes in VR progress test results during the course of rehabilitation (visits 3-32 and 33-62 if a subject repeats rehabilitation).

Exploratory outcome measures will be collected in subjects with restored visual fields. The qualities of recovered visual field will be examined with visual acuity, color recognition, and shape recognition tests after rehabilitation (visit 33 or 63).

Analytical Plan

Results will be analyzed initially using descriptive statistics. The improvement of visual detections will be assessed by using a two-way ANOVA on the percentages of visual detections to stimuli presented in the hemianopic hemifield in the peripheral visual field tests before and after rehabilitation. Comparisons for subjects will be done using chi square tests for proportions, and t-tests or ANOVA procedures for continuous variables. Other inferential statistical analysis will be conducted as appropriate.

Human Subjects Protection

Subject Recruitment Methods

Protocol version: 2

Protocol updated 7.01.20

Subjects with homonymous hemianopia on either the left and right side of the visual field will be recruited using resources from Wake Forest University Health Sciences' Clinical and Translational Science Institute (CTSI). Members of the PI's research team will perform recruitment. Coordination of potential participants' visit will be done by phone or in person conversation or by email.

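### The 3- and 6-month visits are described only for subjects who improved on the VR test, so Aim 2 as written measures durability among improvers, not the long-term effect in all trained subjects

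*Combined protocol and SAP*

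**What the plan says.** Specific Aim 2 is to "Assess the long-term effects of rehabilitation through follow-up visits after the completion of rehabilitation". It is not limited to subjects who respond.

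The route after training depends on the VR progress test:

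- **Improvers (Session 33).** "If a subject shows visual field expansion in the virtual reality visual field progress test, subjects will be given a" frame (peripheral visual field) test and both questionnaires. Shape, acuity and colour tests take place at the same visit, and a Humphrey test follows at Session 34.
- **Non-improvers (Session 63).** "If no visual field improvement (measured by virtual reality visual field progress tests) has occurred at the end of the 2nd round of rehabilitation", then "subjects will complete one last visit, where they will be given the" "NEI VFQ-25 and VA LV VFQ-48 questionnaires to complete". No frame or Humphrey test is listed.
- **Follow-up (Sessions 35 and 36).** "Subjects will complete a follow-up visit 3 months after the end of rehabilitation" and "Subjects will complete a final follow-up visit 6 months after the end of rehabilitation". Each has the frame test and both questionnaires. The text says only subjects, but the last-visit rule leaves no place for non-improvers.

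Session 1 gives everyone the frame test and both questionnaires at baseline. Under Outcome Measures, "The primary outcomes for all participants will be the visual field measurements from Humphrey Visual Field and peripheral frame test", with the after-treatment values at visits 34 and 35, or 63 and 64. The quality-of-life comparison is visit 1 against visit 33 or 63. The Analytical Plan gives descriptive statistics and before/after tests. It has no follow-up analysis, no rule on which subjects enter a follow-up summary, and no handling of missing values.

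**The concern.** Who is measured at 3 and 6 months is decided by a post-treatment outcome. The questionnaires are planned in both routes at the end of training, but only in improvers afterwards. A descriptive table of mean change by visit, which the plan neither specifies nor rules out, would therefore change its population between the post-training and follow-up columns. Part of any apparent retention would then come from who remained, and a real fade in improvers could be masked.

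The protocol says that its findings will be used to design later studies. A durability figure read as the effect in everyone trained would carry forward. The design compares subjects only with their own pre-intervention values, so no untreated group would expose the problem.

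**Working it through.** **The plan's own figure.** Under Sample Size, 80% success with n = 5 is said to give a 95% interval of 0.35 either side. The Wald half-width is 1.96 × √(0.8 × 0.2 / 5) = 0.351, which agrees. The 80% is therefore used below as the share of improvers, which assumes that a successful result means VR improvement.

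**How likely is a non-improver?** The chance of at least one is 1 − 0.8^n: 1 − 0.328 = 67% at n = 5 and 1 − 0.107 = 89% at n = 10. The chance of none at n = 5 is 33%.

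**Questionnaires.** Let p be the share of improvers, G their mean gain, g the mean gain in non-improvers, and r the fraction of G that improvers retain.

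- Post-training mean, all subjects: M = pG + (1 − p)g
- Follow-up mean, improvers only: rG
- Apparent retention: rG / M, against a true retention of r in the same subjects
- Fade hidden behind a flat mean: 1 − M/G

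The documents give none of G, g and r. The table assumes G = 10, g = 0 or 5, and r = 1 (no fade). With five subjects, p = 0.8 is one non-improver and p = 0.6 is two.

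| p | g | Post-training mean | Follow-up mean | Apparent rise | Fade that a flat mean would hide |
|---|---|---|---|---|---|
| 0.8 | 0 | 8 | 10 | 25% | 20% |
| 0.8 | 5 | 9 | 10 | 11% | 10% |
| 0.6 | 0 | 6 | 10 | 67% | 40% |
| 0.6 | 5 | 8 | 10 | 25% | 20% |
| 1.0 | none | 10 | 10 | 0% | 0% |

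If improvers truly lose half their gain (r = 0.5) at p = 0.8, the apparent loss is 1 − 5/8 = 37.5% with g = 0, or 1 − 5/9 = 44% with g = 5.

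**Frame test.** The populations by visit are:

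- Session 1: all subjects
- End of training: improvers only (Session 33), since Session 63 lists no frame test
- Sessions 35 and 36: improvers only

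Membership does not change between end of training and follow-up, so no artefact of this kind arises there. The gap lies against the all-subject baseline, and against a primary outcome declared for all participants.

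**Visit numbers.** Outcome Measures names visits 63 and 64 as after-treatment visits for the primary field outcomes. Session 63 as described has no field test, and no Session 64 is described. Visit 35, named on the other route, is the 3-month follow-up.

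**The case against.** The strongest reply is that no planned quantity is biased. The quality-of-life outcome compares visit 1 with visit 33 or 63, which both routes supply, and no 3- or 6-month mean is specified. Asking whether a gain lasts in those who had one is also a reasonable reading of Aim 2, since the animal work cited under Objectives reports that the expansion persisted. All of this stands. A within-improver change, labelled as such, is valid. What remains is that the aim is worded more widely than the visits allow and that nothing in the plan prevents the misleading comparison.

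Visits 63 and 64 might be thought to supply the missing data. They could equally be the visits of subjects who improve in the second round, because the exploratory tests in subjects with restored fields are also placed at visit 33 or 63. Either way, no follow-up of non-improvers is established. Figure 2 (the timeline) is not reproduced in the text examined and should be checked.

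A reader might infer stronger points that the documents do not support:

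- **That follow-up means are certain to rise.** The result concerns change from baseline and needs improvers to have gained more. Raw score means could fall if a departing subject started high, and nothing shifts if everyone improves.
- **That late follow-up of non-improvers is the only in-trial view of repeat-test drift.** Sessions 1 and 63 already give questionnaire change in these subjects.
- **That an imprecise VR test makes the distortion larger.** Its 30 trials over three angles and two sides are about 5 per location if evenly spread, and no threshold defines improvement. But random misclassification pulls the two groups' mean gains together and shrinks the shift.

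**Conclusion.** The concern holds in a limited form. As written, the 3- and 6-month visits yield results for VR improvers only, and Aim 2 does not say so.

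For the questionnaires, comparing those results with the post-training change in all subjects overstates retention whenever improvers gained more than non-improvers. At the plan's 80% success rate the overstatement is 25% if non-improvers gain nothing and 11% if they gain half as much. Both figures rest on assumed gains, on applying the plan's success rate to the VR criterion, and on no dropout for other reasons. The direction needs only the difference in gain.

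For the frame test, the defect is the missing post-training value in non-improvers, which also reaches the primary outcome. It does not create a spurious change between post-training and follow-up.

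In an exploratory study of this size the point should be corrected, chiefly because the correction is cheap.

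**What to change.** 1. **Reconcile the visit descriptions.** State what visits 63 and 64 contain and for whom, and make this agree with the last-visit rule at Session 63. Include the frame test at the non-improvers' end-of-training visit. Without it they have no field value to pair with a later one. Sessions 35 and 36 fit the frame test and both questionnaires into one hour, and Session 63 is already scheduled for one hour. Say also whether the Humphrey test applies to non-improvers. If it does, that is a further optometrist visit of about an hour.
2. **Invite every trained subject to the existing 3- and 6-month visits.** At 80% success this means about one extra subject of 5 or two of 10 (0.2 × 5 = 1, 0.2 × 10 = 2). The cost is two one-hour visits each at 50 dollars a visit, or 100 to 200 dollars in payments, and some burden on people who did not benefit.
3. **Compare like with like.** In every Aim 2 summary, report change only in subjects measured at both visits, with baseline and end-of-training values recomputed for those same subjects and the number shown at each visit. This costs nothing.

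If non-improvers are not followed, title the Aim 2 result *durability among VR improvers* and do not present it as the long-term effect in all treated subjects.

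### The primary after-treatment visits for one-round subjects (34 and 35) skip the end-of-training frame test at visit 33 and use the 3-month follow-up instead; the two-round visits (63 and 64) are not described as visual field visits

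*Combined protocol and SAP*

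**What the plan says.** In the Outcome Measure(s) section, Humphrey perimetry and the frame test are both primary, and for every participant. The visits to be compared are set in these words: "with comparisons made before (visits 1 and 2) and after treatment (visits 34 and 35 or visits 63 and 64").

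The Interactions section gives those visit numbers their content:

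- Visit 1 includes the baseline frame test (the peripheral visual field test). Visit 2 is the baseline Humphrey test, which may be replaced by a recent result.
- Visits 3 to 32 are training.
- "Study Session 33: Post Rehabilitation Tests - Subject visual field increase (1.5 hours"): frame test, both questionnaires, and the acuity, shape and color tests. The frame test there is conditional; the sentence that schedules it opens "If a subject shows visual field expansion in the virtual reality visual field progress test, subjects will be given a".
- "Study Session 34: Humphrey Visual Field Post-Intervention Test (1 hour").
- "Study Session 35: 3 Month Post-Intervention Follow-up Tests (1 hour"). Its content is given as follows: "The follow-up visit will consist of a peripheral visual field test, and NEI VFQ-25 and VA LV VFQ-48 questionnaires". There is no Humphrey test. Visit 36, at 6 months, has the same content.
- Visit 63 is described only for subjects with no improvement after a second round. It is their last visit and consists of the two questionnaires.

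In the Outcome Measure(s) section, second-round training occupies visits 33 to 62. The questionnaire outcome and the exploratory outcomes take visit 33 or 63 as the post-treatment visit. Specific Aim 2 is to "Assess the long-term effects of rehabilitation through follow-up visits after the completion of rehabilitation". The Analytical Plan compares frame-test detection before and after training with a two-way ANOVA and gives no visit number.

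**The concern.** In this single-group before/after study, the visit that counts as after defines the primary result. Aim 1 (efficacy) and Aim 2 (long-term effects) use the same frame test and are separated only by when it is done. Taking visit 35 for the primary comparison means that the frame-test result reported for Aim 1 combines the training effect with whatever is kept or lost over the next 3 months. The test done at the end of training, which answers Aim 1 directly, is then collected but assigned to no outcome.

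The Analytical Plan does not settle the matter. An analyst could use visit 33 (consistent with the other outcomes) or visit 35 (the literal text) and defend either, and that choice could be made after the data are seen. A subject who attends visit 33 but not visit 35 would, on the literal rule, have no primary frame-test result even though one had been measured.

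**Working it through.** **Inputs.** Visit contents come from the Study Session headings under Interactions. The outcome visits and the second-round range (33 to 62) come from Outcome Measure(s).

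**The plan's own figure.** The only computed design figure is the confidence-interval half-width under Sample Size: 1.96 × √(0.8 × 0.2 / 5) = 0.3506, which reproduces the stated 0.35. It does not depend on visit numbers and does not change.

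**Step 1: length of each round.** Round 1 is 32 − 3 + 1 = 30 sessions. Round 2 is 62 − 33 + 1 = 30 sessions. A second round therefore adds 30 to every later visit number.

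**Step 2: position after the last training session.**

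- One-round primary pair: 34 − 32 = 2 and 35 − 32 = 3, the second and third visits after training.
- Two-round primary pair: 63 − 62 = 1 and 64 − 62 = 2, the first and second visits after training.
- Questionnaire and exploratory outcomes: 33 − 32 = 1 and 63 − 62 = 1, the first visit after training in both cases.

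The two primary pairs do not follow one rule. The secondary and exploratory visits do.

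**Step 3: visit by visit.**

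| Scheduled content, one round | One-round visit | Same position after two rounds (+30) | Named as a primary after-treatment visit |
|---|---|---|---|
| Frame test and questionnaires (field increased) | 33 | 63 | two-round only |
| Humphrey | 34 | 64 | both |
| Frame test and questionnaires, 3 months | 35 | 65 | one-round only |
| Frame test and questionnaires, 6 months | 36 | 66 | neither |

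The one-round match to 63 and 64 is 33 and 34. The two-round match to 34 and 35 would be 64 and 65. The +30 column gives positions only; the documents do not say that these tests are done at those visits.

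**Step 4: order of tests.** At baseline the order is frame test (1), then Humphrey (2). Visits 33 and 34 repeat it. Visits 34 and 35 reverse it.

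**Step 5: which measure moves.** With 34 and 35, Humphrey stays at its post-intervention visit. Only the frame test moves, from the first visit after training to 3 months after it.

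**Step 6: two-round subjects.** The described visit 63 contains neither primary test and is the last visit for non-improvers. Visit 64 is not described in the readable text. For two-round subjects who do improve, the only post-training content given is the questionnaires and exploratory tests at visit 33 or 63. Yet the primary outcome is stated for all participants.

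**The case against.** The strongest reply is that this is a numbering slip and that the rest of the protocol shows the intent. Visit 33 gives the frame test expressly to measure field expansion, the other outcomes use 33 or 63, and the ANOVA is before against after training. That is probably right, and it supports the correction. It does not remove the error, because the sentence containing the slip is the one that defines the primary time point, and nothing in the readable text overrides it. The study is also exploratory and small, which limits the consequences but does not settle which test is primary.

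Several stronger readings are tempting, and the documents do not support them:

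- *Efficacy as a whole is read 3 months late.* Humphrey is also primary and is at visit 34. Only the frame-test half is late.
- *Two-round subjects are read immediately, so fast responders look worse than slow ones.* No frame test is described at visit 63 and visit 64 is undefined, so an immediate reading is inferred from numbering alone. No such comparison is planned either. For non-improvers the problem is a missing primary measurement, not its timing.
- *Losing one subject between visits 33 and 35 costs a fifth of the data.* The 5 subjects hoped for are those who complete every session. A one-round subject among them has attended visit 35 by definition.
- *The gain fades by some stated amount.* The protocol gives no human durability figure. Its only evidence is persistence in cats tested at 12 to 21 months.
- *Aim 2 loses its reference point.* The visit 33 frame test is still collected, and the design compares with pre-intervention measures, so persistence can be judged from baseline.

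**Conclusion.** Wrong as written. For one-round subjects the primary after-treatment pair is shifted by one visit against the schedule, against the two-round pair and against the other outcomes. Followed literally, one of the two primary measurements is taken 3 months after training instead of at its end, and the visit 33 frame test is left outside every outcome. The effect on the observed gain cannot be sized from the documents, since it depends on how well the gain holds in humans, which is what Aim 2 is meant to find out.

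That 33 and 34 were intended is an inference from the 30-visit offset, the visits used for the other outcomes and the order of the baseline tests. It is strong but not confirmed. A reader might take 34 and 35 as a deliberate choice of a durable endpoint; the text does not present it so, and the pair 63 and 64 contradicts it.

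For two-round subjects the conclusion is narrower: the outcome section relies on visits at which the readable text schedules no visual field test. Figure 2, the study timeline, is not shown and may define them.

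**What to change.** 1. In Outcome Measure(s), change the one-round primary after-treatment visits to 33 (frame test) and 34 (Humphrey), saying which test belongs to which visit. Use the same visit numbers in the Analytical Plan.
2. Assign visits 35 and 36 to Aim 2 as the 3-month and 6-month outcomes for the frame test and questionnaires, and state the reference (baseline, end of training, or both). At present no outcome names visit 36.
3. Reconcile the Study Session descriptions with Outcome Measure(s) for two-round subjects. State what is measured at visits 63 and 64 for improvers and for non-improvers, and number any follow-up visits separately, since 33 to 36 are training sessions for anyone who repeats. Either the primary tests are scheduled for every subject to whom the primary outcome applies, or the outcome should no longer be stated for all participants.

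Items 1 and 2 are wording changes that need no new test for one-round subjects who show expansion, because these tests are already scheduled for them. Item 3 is wording only if Figure 2 or the operating procedures already provide for the tests. Otherwise it may add a frame test and a Humphrey visit for some two-round subjects.

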Grating Acuity Test - Visual acuity will be tested using a standard grating test. Subjects will be presented with a 10°x10° square window filled with either a horizontal or vertical grating, located 5° from the fixation point on a computer screen in their hemianopic or intact side. Gratings will start from 0.2 cycles per degree and progress to larger sizes of 0.5, 1.0, 1.5, 2.0, 2.5, 3.0, 4.0, then 5.0 cycles per degree. The test will comprise of 5 trials for each grating. Subjects will be asked to identify whether the grating is horizontal or vertical by either pushing buttons on a response pad or verbally. Responses will be recorded for each question.

Virtual Reality (Visual Field) Progress Test - At the end of each rehabilitation session, subjects will perform a brief 5-minute test using the VR system to

Color Vision Test - The color vision test will be administered on a computer. While focused on a central fixation point, subjects will be presented with a colored $10^\circ \times 10^\circ$ block located 5° in the anopic hemifield and be asked to verbally identify the color. A member of the research team will record these responses. The color in each trial will be randomly picked among the color choices of white, black, red, orange, yellow, green, blue, and violet. Each color will be displayed at least 3 times.

Shape Recognition Test - Subjects will be presented with basic shapes in their hemianopic side on a computer monitor. Shapes will be colored black and be displayed on a white background in a $10^\circ \times 10^\circ$ square window located 5° in the previously hemianopic side. Subjects will be asked to fixate on a central point and verbally identify each object or express uncertainty. Verbal responses will be recorded for later analysis. During this test, subject responses may be audiotaped in order to capture their responses. This test will consist of 20 trials.

Questionnaires

The NEI VFQ-25 and VA LV VFQ-48 questionnaires are designed to assess the taker's quality of life regarding limitations due to low vision.

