During this visit, baseline measurements for subjects will be obtained. Subjects will undergo a peripheral visual field test and be asked to complete 2 quality of life questionnaires: the National Eye Institute Visual Function Questionnaire (NEI VFQ-25) and the Veterans Affairs Low Vision Visual Function Questionnaire (VA LV VFQ-48). Subjects are expected to spend up to 2 hours for this visit.

(Optional) Study Session 2: Pre-Intervention Test - Humphrey Visual Field Test (1 hour)

Subjects will report to an optometrist, who will administer the Humphrey Visual Field Test, using a size V stimulus. This visit will be separate from the other pre-intervention tests due to the special equipment needed for the Humphrey Visual Field Perimetry. This visit is expected to take up to 1 hour. This visit may be omitted if subjects have a recent Humphrey Visual Field Perimetry test result and gives the study team permission to view and keep a copy of the result.

Study Sessions 3 – 32: Cross-Modal Rehabilitation Training (30 minutes each day)

Each cross-modal rehabilitation training session will take place either on the Wake Forest Baptist Medical Center Campus or in subjects' homes, if subjects find traveling to the Wake Forest campus to be too difficult to do daily. For patients who are performing rehabilitation at home, the study team will regularly call and check-in with the subject in order to make sure the patient is not experiencing any problems. The VR rehabilitation system will send data such as duration of rehabilitation and progress test results through a cellular network, in order to monitor compliance and track rehabilitation progress. The data will only be linked to a study identifier to maintain privacy. Initial rehabilitation sessions will be done at the Wake Forest Baptist Medical Center campus to ensure subjects understand how to use the rehabilitation device and are capable of performing rehabilitation at home.

In each rehabilitation session, subjects will sit down, put on a virtual reality headset with a pair of headphones, and use a button on a handheld controller to interact with the rehabilitation system. In order to make sure subjects are correctly performing rehabilitation, the headset may be outfitted an eye tracking system consisting of a camera and low intensity infrared lights to collect data on patient's eye movements.

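### Acuity, colour and shape are tested near fixation only after training, so a good score on the hemianopic side cannot be separated from residual ability

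*Combined protocol and SAP*

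**What the plan says.** Pre-training assessment is described in two places. At Study Session 1, "Subjects will undergo a peripheral visual field test and be asked to complete 2 quality of life questionnaires". Study Session 2 is Humphrey perimetry, and "This visit may be omitted if subjects have a recent Humphrey Visual Field Perimetry test result". Neither session includes an acuity, colour or shape test.

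Those tests first appear at Study Session 33, for subjects whose virtual reality progress test shows field expansion. That visit adds a "shape recognition test, visual acuity test, and color vision test". Outcome Measure(s) agrees on timing (after rehabilitation, visit 33 or 63) and on who is tested: "Exploratory outcome measures will be collected in subjects with restored visual fields". The 3-month and 6-month follow-up visits do not repeat them.

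The stated reason is a hypothesis that the pathway behind the restored vision may be less capable than the cortex it replaces, so that "recovered vision may have lower visual acuity". All three tests use a 10° by 10° window or block at 5°. The shape window is "located 5° in the previously hemianopic side". Gratings are described for both sides, colour and shape for the hemianopic side only.

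The Design section says the study will "compare results against measures from patients pre-intervention". There is no control arm.

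**The concern.** Calling a measured ability recovered implies that it was absent before. The shape test's description presumes this of the tested location, but the plan does not check it for acuity, colour or form. The eligibility criteria require a diagnosis of homonymous hemianopia and a qualifying lesion. They set no minimum depth or extent of loss and no limit on central sparing. Study Session 1 itself accepts that effects vary between patients.

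If some subjects could already use the strip of field next to fixation, their good post-training scores would be read as properties of restored vision. The Sample Size section says the findings will be used to design future studies, so the error could carry forward.

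**Working it through.** **Plan's own figure.** The plan gives no precision or target for these outcomes. Its only precision figure, a half-width of 0.35 for a success proportion of 0.80 with n = 5, reproduces as 1.96 × √(0.8 × 0.2 / 5) = 0.351. This point does not depend on it.

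**Where the window lies.** A 10° window at 5° spans 0° to 10° if 5° is its centre, and 5° to 15° if 5° is its near edge. The protocol does not say which.

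**What is measured there before training.**

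| Measurement | Locations | Ability measured | Covers the window? |
|---|---|---|---|
| Peripheral visual field test (Session 1) | 15°, 30°, 45°, 60°, 75° | Light detection | No; at most its outer edge |
| Humphrey perimetry (Session 2 or a recent result) | Up to 30° | Light detection | Yes, for light only |
| Virtual reality progress test (end of each training session) | 15°, 30°, 45° | Stimulus detection | No; at most its outer edge |
| Grating, colour and shape tests | 5° window | Acuity, colour, form | Not given before training |

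So 0 of 3 capability tests have a baseline. A subject can also qualify for them through expansion at 15° or beyond and then be tested closer to fixation, where vision may not have been lost.

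**How misleading a post-only score could be.** This is an illustration; the residual rates and the cut-off of 12 correct out of 20 shapes are assumptions. If training adds nothing and the subject's accuracy is r throughout, then P(at least 12 of 20) = Σ C(20,k) r^k (1 − r)^(20−k), summed over k = 12 to 20.

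| Residual accuracy r | P(at least 12/20) with no gain |
|---|---|
| 0.20 | 0.0001 |
| 0.40 | 0.057 |
| 0.60 | 0.60 |
| 0.70 | 0.89 |

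A good score points to recovery only if residual accuracy is known to be low, and the plan does not measure it. More subjects would not help, because gain is not identifiable from post-training scores at any sample size.

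**Time to add a baseline.** Gratings: 9 frequencies × 5 trials × 2 sides = 90, assuming 5 trials per frequency on each side. Colour: 8 × 3 = 24 at minimum. Shape: 20. Total: 134. The training description gives 200 trials in about 30 minutes, so 1,800 s / 200 = 9 s per trial. Then 134 × 9 s = 1,206 s, about 20 minutes. As a second estimate, Session 33 (1.5 h) contains the same tests as each follow-up visit (1 h) plus these three, which implies about 30 minutes.

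**The case against.** The strongest case against is that the plan asks a narrower question. The hypothesis at Session 33 is that recovered vision falls short of cortical vision, and the animal precedent compares rehabilitated with intact animals (2 versus over 5 cycles/degree). The human counterpart is the hemianopic side against the intact side, and gratings are described for both. A poor post-training score is also informative alone, since it shows that the tested side lacks that ability. Outcome Measure(s) does not define these outcomes as change. All of this stands, and it limits the point to crediting a good score to recovery.

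The Humphrey baseline is a partial safeguard, because it can show whether light was detected around 5°. It does not measure acuity, colour or form, an earlier result may replace it, and no rule links it to where the window is placed.

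Four stronger readings are tempting, and the documents do not support them.

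- **That the Design section promises a baseline comparison of visual capabilities.** The comparison with pre-intervention measures is in one sentence, and visual capabilities are listed as something to assess in the next. Joining them is a natural inference, not an explicit commitment, and the term is not defined as these three tests.
- **That these tests can support no statement about acuity, colour or shape.** The grating comparison and poor scores can.
- **That subjects do have spared central vision.** The protocol gives no rate of sparing; it only leaves the possibility open.
- **That guessing is the difficulty.** Chance levels are fixed reference points and do not depend on a baseline.

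**Conclusion.** The point holds for one inference. A good post-training colour, shape or hemianopic-side acuity score cannot be separated from residual ability and should not be reported as recovered. All three tests are affected, in every subject who takes them. How often the conclusion would be wrong depends on residual ability near fixation, which the documents do not give; in the shape illustration the chance of a misleading score runs from almost nothing to 0.89.

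The study timeline figure is not available here, so the finding rests on the session text, which is specific and lists no baseline administration.

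Severity is low. These outcomes are exploratory in a proof-of-concept study recruiting 10 subjects. The primary and secondary outcomes have baseline or serial measurements, and no efficacy conclusion depends on these tests.

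**What to change.** Give the same three tests once before training begins, at Session 1 or at an initial on-campus training session. Test the hemianopic side for all three, and the intact side for gratings as already planned. Report within-subject change alongside the post-training score, and state whether 5° is the window's centre or near edge.

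With 5 completers, the 95% t-interval half-width for a mean change is 2.776 / √5 = 1.24 SD of the change (2.262 / √10 = 0.72 SD with 10). The change scores are therefore descriptive, but they would show what each subject could do beforehand.

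The cost is about 20 to 30 minutes of subject time and one practice exposure, with the same tests, no new equipment and no new staff. Session 1 is already up to 2 hours, so its stated length would need revising if the tests go there. If no baseline is taken, label the results post-training function, not recovered function.

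In the same edit, reconcile the visit numbers: Outcome Measure(s) allows these tests at visit 63, while Study Session 63 is described as a questionnaire visit for subjects without improvement.
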